5.1. Sample Size

The primary aim of this study is to assess the difference in outpatient post-surgical costs between the control and intervention groups. The exact post-procedure cost estimates under study are unknown; however, we can estimate that an effect size of approximately 0.33 can be detected with 150 subjects per group with at least 80% power. The effect size is the ratio of the mean difference over the standard deviation (SD) assumed for each population, while the coefficient of variation (CV) is the ratio of the population mean over the SD. Lower variability would enable detection of a smaller cost difference, or the detection of a larger difference with fewer patients. The below table gives several mean ratios that could be detected with 80% power and 300 subjects where R1 is the ratio of the means (Control / Intervention) at which the power is calculated using a two-sample t-test with equal variance and a significance level of 0.05.

Power	N1	N2	N	R0	R1	Effect		
						Size	CV	Alpha
0.8023	150	150	300	1.000	1.033	0.3255	0.1	0.050
0.8070	150	150	300	1.000	1.067	0.3275	0.2	0.050
0.8003	150	150	300	1.000	1.100	0.3247	0.3	0.050
0.8045	150	150	300	1.000	1.134	0.3264	0.4	0.050
0.8184	150	150	300	1.000	1.170	0.3324	0.5	0.050
0.8101	150	150	300	1.000	1.200	0.3288	0.6	0.050
0.8078	150	150	300	1.000	1.230	0.3278	0.7	0.050
0.8096	150	150	300	1.000	1.260	0.3286	0.8	0.050
0.8143	150	150	300	1.000	1.290	0.3306	0.9	0.050
0.8209	150	150	300	1.000	1.320	0.3335	1.0	0.050
0.8098	150	150	300	1.000	1.340	0.3287	1.1	0.050
0.8025	150	150	300	1.000	1.360	0.3256	1.2	0.050
0.8153	150	150	300	1.000	1.390	0.3310	1.3	0.050
0.8125	150	150	300	1.000	1.410	0.3298	1.4	0.050
0.8116	150	150	300	1.000	1.430	0.3295	1.5	0.050
0.8123	150	150	300	1.000	1.450	0.3297	1.6	0.050
0.8004	150	150	300	1.000	1.460	0.3247	1.7	0.050
0.8039	150	150	300	1.000	1.480	0.3262	1.8	0.050
0.8082	150	150	300	1.000	1.500	0.3280	1.9	0.050
0.8007	150	150	300	1.000	1.510	0.3248	2.0	0.050

Thus, with 300 subjects we can detect an effect size of 0.33 which represents a whole scenario of cost differences that can be detected with at least 80% power that is dependent on the variability of the costs under study. The below table illustrates some example cost differences that could be detected based on the assumed SD of the costs.

Standard Deviation (SD)	Mean Cost Difference (\$)	Standard Deviation (SD)	Mean Cost Difference (\$)
100	32.50	800	259.60
200	64.90	900	292.10
300	97.40	1000	324.50

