6.2 Study Objectives

6.2.1 Primary Objective:

The primary objective is to compare the effects of tele-rehab-supported PT versus traditional home and/or clinic-based PT for TKR on health service use costs at 12-weeks postoperative.

Hypothesis (Superiority Test): Patients who receive tele-rehab-supported PT will have lower total episode of care costs compared with patients in the traditional PT group at 12-weeks.

6.2.2 Secondary Objective:

The secondary objectives are to compare tele-rehab-supported PT and traditional PT on patient-centered outcomes as follows:

- a. Effectiveness hypothesis (Non-Inferiority Test): The tele-rehab intervention will be non-inferior to traditional PT at 6 weeks (differences between groups <5% for clinical and patient-reported outcomes) and 12 weeks (difference <5% patient-reported outcomes).
- b. Safety hypothesis (Non-Inferiority Test): The tele-rehab intervention will be non-inferior to traditional PT at 12 weeks (pain, falls, and self-reported number of re-hospitalizations).

6.2.3 Exploratory Objectives:

The final objectives (exploratory analyses) are to determine if superiority between PT methods exist for the endpoints primarily tested for non-inferiority, determine whether individual patient characteristics are associated with differential improvement from 6 to 12 weeks assessed by patient-reported outcomes, and to determine the cost for the VERA system such that the cost between the control group and intervention groups is cost-neutral, assuming that the intervention group is determined to cost less.

7 Study Design

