9.9 Power and Sample Size Calculations

The primary aim of this study is to assess the difference in outpatient post-surgical costs between the control and intervention groups at 12-weeks post-operative. The exact post-procedure cost estimates under study are unknown; however, we can estimate that an effect size of approximately 0.33 can be detected with 150 subjects per group with at least 80% power. The effect size is the ratio of the mean difference over the standard deviation (SD) assumed for each population. Lower variability would enable detection of a smaller cost difference, or the detection of a larger difference with fewer patients. The sample size estimates were made assuming a two-sample t-test with equal variance and a significance level of 0.05. Thus, with 300 subjects we can detect an effect size of 0.33 which represents a whole scenario of cost differences that can be detected with at least 80% power that is dependent on the variability of the costs under study. The below table illustrates some example cost differences that could be detected based on the assumed SD of the costs.

Standard Deviation (SD)	Mean Cost Difference (\$)	Standard Deviation (SD)	Mean Cost Difference (\$)
100	32.50	800	259.60
200	64.90	900	292.10
300	97.40	1000	324.50
400	129.80	1100	357.00
500	162.30	1200	389.50
600	194.70	1300	421.90
700	227.20	1400	454.40
750	243.40	1500	486.80

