9.10 Primary Effectiveness Analysis

The total health service use costs at 12-weeks post-operative will be compared between patients who receive tele-rehab-supported PT (virtual group) versus traditional home and/or clinic-based PT (control group) for TKR. The primary cost comparisons will be done using an analysis of variance (ANOVA) method for continuous variables if (1) the dependent variable is normally distributed or (2) can be normalized using a transformation such as the logarithm or square root. The underlying assumptions of the statistical test procedure will be verified through non-normality tests and plots. If there is strong evidence that the assumptions are not met or cannot be met with an appropriate distribution, the nonparametric Wilcoxon Rank sum test will be used.

The total health service use costs at 12-weeks post-operative will be the primary effectiveness endpoint for this study. This will be calculated using a fee-for-service model and assigned costs. Tele-health for rehabilitation services was not a reimbursable service at the start of the trial, and thus a total intervention cost, including direct and indirect time with physical therapy and any in-person visits, is assigned using the following units and costs:

Healthcare Encounter	Unit	Cost
Intervention	Total (all interactions)	\$600
Home health PT	<5 visits (cost per visit) ≥5 visits (single cost per 60-day episode)	\$133 \$2,325
Outpatient clinic PT	Single visit	\$90
PT call/email	Single interaction	n/a
Doctor's office	Single visit	\$150
Doctor's office call/email	Single interaction	n/a
Urgent care or ER visit	Single visit	\$250
Re-hospitalization	Full length of one inpatient stay	\$7,825
Inpatient rehab facility	Full length of stay	\$10,720
Skilled nursing facility	Full length of stay	\$6,510

Intervention Group Patients: Total costs will be calculated as the assigned cost of the intervention plus assigned costs for any reported doctor's office visits, urgent care or ER visits, re-hospitalizations, and inpatient rehabilitation or skilled nursing facility stays in the 12 weeks following discharge from the surgical hospital stay. The formula is as follows:

Cost = intervention cost + (# of doctors office visits * \$150) + (# of ER/UC visits * \$250) + (# of re-hospitalizations * \$7,825) + (# of skilled nursing facility stays * \$6,510) + (# of inpatient rehabilitation facility stays * \$10,720)

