The null hypothesis for the primary endpoint is that there is no treatment difference between patients who receive tele-rehab-supported PT versus traditional home and/or clinic-based PT. The alternative hypothesis is that a treatment difference exists between patients who receive tele-rehab-supported PT versus traditional home and/or clinic-based PT.

Let μ_T and μ_C be the average total health care costs for the virtual and control PT groups, respectively. The null hypothesis and the alternative hypothesis will be as follows:

$$\begin{aligned} H_0: \mu_T &= \mu_C \\ H_A: \mu_T &\neq \mu_C \end{aligned}$$

The primary statistical method for the hypothesis test will be t-test, and the mean difference between groups will be presented with a 95% confidence interval (CI). The test is two-sided even though we are more interested in determining that the intervention group is superior to the control group to allow for a possible negative significant difference.

Let \bar{X}_T and \bar{X}_C be the sample mean costs for the virtual and control groups, respectively, and let S_T^2 and S_C^2 be the sample variance for the virtual and control samples, respectively. The equality of the variances of the two samples will be tested using the Folded F-test (i.e., $F = \text{Max}(S_T^2, S_C^2)/\text{min}(S_T^2, S_C^2)$). If there is not strong statistical evidence to say that the variances of the two samples are different (insignificant F-test and 4-fold variance difference), then the alternative hypothesis for total cost will be concluded when the associated t-test statistic assuming equal variance is less than the 2.5th percentile of the Student's t distribution with $n_T + n_C - 2$ degrees of freedom, where n_T is the number of subjects in the virtual group and n_C is the number of subjects in the control group. Otherwise, the t-test will be computed assuming the variances are unequal.

If a parametric method is determined not to be possible through normality checks (Shapiro-Wilks test) or transformations, a Wilcoxon rank-sum test will be performed for the primary effectiveness endpoint and a 95% CI for the median difference presented.

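### The primary hypothesis concerns mean cost, but normality checks can move the primary test to a log, square-root or rank test that does not test mean cost

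*SAP*

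**What the plan says.** The primary objective (SAP 6.2.1) is that tele-rehab patients "will have lower total episode of care costs compared with patients in the traditional PT group at 12-weeks". SAP 9.10 defines the two parameters to "be the average total health care costs for the virtual and control PT groups, respectively", sets them equal under the null and unequal under the alternative, and continues: "The primary statistical method for the hypothesis test will be t-test, and the mean difference between groups will be presented". A 95% interval accompanies that difference.

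The power basis is the same. SAP 9.9: "The sample size estimates were made assuming a two-sample t-test with equal variance and a significance level of 0.05". Protocol 5.1: "R1 is the ratio of the means (Control / Intervention) at which the power is calculated using a two-sample t-test with equal variance".

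SAP 9.10 also opens two other routes for the same primary test. One is an analysis of transformed cost, if cost "can be normalized using a transformation such as the logarithm or square root". The other is the rank test: "If a parametric method is determined not to be possible through normality checks (Shapiro-Wilks test) or transformations, a Wilcoxon rank-sum test will be performed". The SAP applies this second route, with its own summary measure, "for the primary effectiveness endpoint and a 95% CI for the median difference presented". Protocol 5.2 has the same switch. SAP 9.10 asks for strong evidence, from tests and plots, before the rank test is used. It gives no threshold and does not say whether the check is pooled or by arm.

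**The concern.** The formal hypotheses appear once, in means. No hypothesis, back-transformation or reporting scale is given for the transformed test, and the rank branch receives only an interval for a median difference.

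A claim about total cost follows the mean. Here the mean is driven by a few large items: $7,825 per re-hospitalization, $6,510 or $10,720 for facility stays, and $2,325 for a home-health episode. A rank test gives these little weight. Two errors follow. A real saving from fewer home-health episodes can be missed or reversed. Or cheaper routine PT can look like a saving when extra inpatient stays have cancelled it. SAP 9.12 later derives a break-even VERA price from average cost, so the primary p-value and that price could answer different questions.

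A separate drafting fault sits in the same section. Under the equal-variance rule, the alternative is concluded only when t falls below the lower 2.5% point. That contradicts the two-sided alternative stated just above it and the two-sided convention for superiority in SAP section 9.

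**Working it through.** **1. The plan's own power figures reproduce.** The dollar table is 0.3245 × SD (0.3245 × 1,500 = 486.75, tabulated as $486.80). The ratio table in Protocol 5.1 follows ln(R1)/√ln(1+CV²) with one common CV:
- ln(1.033)/√ln(1.01) = 0.3255, power 0.8023
- ln(1.32)/√ln(2) = 0.3335, power 0.8209
- ln(1.51)/√ln(5) = 0.3248, power 0.8007

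All 20 rows agree. The ratio table is therefore a log-scale calculation. It speaks to mean cost only if log cost has the same spread and shape in both arms.

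**2. Cost model.** Unit costs are from SAP 9.10. Event rates are assumed, because the documents give none. The control-arm formula was not in the text available, so that arm is rebuilt from the unit-cost table. With 150 per arm:
- Control = 2,325·Bern(h) + 90·V + 150·Pois(2) + 250·Pois(0.03) + 7,825·Bern(rC)
- Tele-rehab = 600 + 150·Pois(2) + 250·Pois(0.03) + 7,825·Bern(rT)

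Clinic visits V are Poisson, or negative binomial of size 3 or 1.5. Protocol 1.1 and 3.4.2 (variable provision, no limit on encounters) make the wider spreads plausible.

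**3. Case 1: equal 3% re-hospitalization, h = 0.20, mean 5 visits.**
- Control mean = 465 + 450 + 300 + 7.5 + 234.75 = $1,457
- Tele-rehab mean = 600 + 300 + 7.5 + 234.75 = $1,142
- True saving = $315

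Hand check of Welch power for Poisson visits. The tele-rehab variance is 45,000 + 1,875 + 7,825²·0.03·0.97 ≈ 1,828,700. Control adds 2,325²·0.20·0.80 + 90²·5 = 905,400, giving 2,734,100. SE = √(4,562,800/150) ≈ 174.4, and 315/174.4 = 1.81, so power is about 44%.

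The rank test goes the other way because 80% of controls have no home-health episode, and their PT averages $450 against $600.

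**4. Case 2: same PT use, means made equal** with rT = 0.03 + 315/7,825 = 0.070.

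**5. Case 3: opposite direction**, h = 0.10, mean 8 visits, rC = 0.03, rT = 0.03 + 352.5/7,825 = 0.075. Both means are $1,495.

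Share of trials significant in the stated direction (4,000 trials per setting; 3,000 in Case 2). Triples are Poisson / size 3 / size 1.5:

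| Case | Truth | Direction | Wilcoxon | Log t | Welch |
|---|---|---|---|---|---|
| 1 | tele-rehab $315 cheaper | control | 16 / 14 / 18% | – | – |
| 1 | same | tele-rehab | 0.3 / 0.5 / 0.3% | – | 46 / 45 / 43% |
| 2 | equal means | control | 32 / 29 / 37% | 7 / 19 / 38% | 2.0 / 2.3 / 2.2% |
| 3 | equal means | tele-rehab | 93 / 40 / 10% | 32 / 4.5 / 0.6% | 3.5 / 2.9 / 2.9% |
| 3 | same | control | – | 0.1 / 1.1 / 7.7% | – |

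The nominal rate per side under equal means is 2.5%. Visit SDs are 2.2/3.7/4.7 in Cases 1 and 2, and 2.8/5.4/7.1 in Case 3. In the Poisson version of Case 3 the log-SDs are 0.61 and 0.64, so near-equal log variance does not protect the log test when the shapes differ. Pooled and Welch rates agreed within 0.001, so nothing depends on the F-test step.

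**6. Case 4: lognormal cost, equal means.** With a common CV of 1.0, log t and Wilcoxon stay at 2.6% to 3.3% per side: no distortion. With CV 1.37 in tele-rehab and 1.0 in control, the ratio of geometric means is √(2/2.877) = 0.83. They then favour tele-rehab in 39% (log t) and 37% (Wilcoxon) of trials; Welch does so in 3.5%.

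**7. Is the rank branch reached?** In Cases 1 and 3, Shapiro-Wilk on pooled residuals rejected raw, log and square-root cost in all 500 trials checked per setting. This is not a switch rate, because plots and judgement also enter, but such data would readily supply the evidence asked for.

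**The case against.** The strongest reply has five parts.

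- **The switch is pre-specified**, and the rank branch names its own estimate. True, but pre-specification does not make a rank test a test of mean cost.
- **Other displays would expose a conflict:** arm means (SAP 9), the re-hospitalization safety comparison (9.11.2), and the exploratory site-adjusted model and break-even analysis (9.12). They would help a reader, but none controls the primary p-value.
- **The reversal in Case 1 is local.** It needs routine control PT below the $600 fee, that is, fewer than 600/90 = 6.7 visits. Under that model with 20% home health, Wilcoxon favours control in 17% of trials at a mean of 5 visits, 0.1% to 1.5% at 6, and none at 7. This stands, but it cuts both ways. At 4 visits, where the true saving is 465 + 360 − 600 = $225, Wilcoxon favours control in 69% to 82%. At 30% home health and 5 visits reversal is rare (0.3%), yet Wilcoxon finds the saving in only 19% to 20%, against 84% to 87% for Welch.
- **Cases 2 and 3 need a 4.0 to 4.5 point excess of re-hospitalization** under tele-rehab. SAP 7.1 says the arms do not differ in risk, and nothing in the documents suggests such an excess. This stands: 93% is an upper-end case and falls to 10% at the widest visit spread.
- **The model is partial.** Facility stays and the $133 home-health tier are not simulated. This also stands. The results show what can happen and are not a forecast.

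The branches can also agree. With half of controls on home health, a mean of 8 clinic visits and 5% re-hospitalization in both arms, every test found tele-rehab cheaper in all simulated trials.

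**Conclusion.** The point holds and should be settled before analysis. That the hypotheses and the permitted tests differ is plain from the text and needs no assumption. How far they diverge rests on assumed rates: from none (lognormal cost with a common CV, or a large home-health difference) to a significant result against a true saving, or a declared saving where mean costs are equal. The false-saving direction depends on excess re-hospitalization or on unequal spread between arms; the missed or reversed saving does not. Because this is the sole primary conclusion and its direction can change, it is more than a reporting matter. The stated 80% power is not in error.

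**What to change.** Make the difference in arithmetic mean cost the primary analysis whatever the normality result: a Welch t-test on dollars, with a bootstrap 95% interval in support. Make the Wilcoxon and transformed-scale tests supportive. If the team prefers another test as primary, restate the hypotheses on the quantity it tests, redo the power calculation, and draw no conclusion on average cost from it. Separately, correct the equal-variance rule to reject when |t| exceeds the 97.5th percentile, with direction read from the interval.

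The cost is SAP wording plus a power change that can go either way (power for a true saving, 150 per arm, mean 8 clinic visits):

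| Setting | Visit SD | Welch | Wilcoxon |
|---|---|---|---|
| $352 saving, 3% re-hospitalization in both arms | 2.8 | 56% | 99% |
| same | 5.4 | 54% | 69% |
| same | 7.1 | 55% | 28% |
| $352 saving, 5% in both arms | 2.8 | 41% | 99% |
| same | 7.1 | 40% | 26% |
| $818 saving, 30% home health | 2.8 | 99% | 100% |
| same | 7.1 | 99% | 98% |

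Welch power below 80% at $352 is consistent with the plan's own table, which needs $486.80 at an SD of $1,500.

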9.11 Secondary Analyses for Effectiveness and Safety

The secondary effectiveness and safety endpoints will include both clinical and patient-reported outcomes at 6-weeks and 12-weeks postoperatively. The secondary objectives are to compare tele-rehab-supported PT and traditional PT on patient-centered outcomes as follows.

9.11.1 Effectiveness hypothesis (Non-Inferiority Test)

The tele-rehab intervention will be non-inferior to traditional PT at 6 weeks (differences between groups <5% for clinical and patient-reported outcomes) and 12 weeks (difference <5% patient-reported outcomes). The secondary objectives are to compare tele-rehab-supported PT and traditional PT on patient-centered outcomes as follows:

- 6 Weeks:
 - KOOS: Total score based on a normalized scale of 0-100 (worst to best). The minimal perceptible clinical improvement difference (MCID) for non-inferiority that we will use is 10 points.
 - ROM: This is reported to reflect both extension (lower) and flexion (upper) range of motion. An MCID is not available and based on recent literature we will use 6.3 degrees for extension and 9.6 degrees for flexion.
 - Gait Speed (m/sec): MCID is 0.1 m/s
- 12 Weeks:
 - KOOS: The minimal perceptible clinical improvement difference (MCID) for non-inferiority will be 10 points.

Analyses for each endpoint will be similar to those considered in Section 9.10 for the primary cost endpoint, except the tests will be one-sided for non-inferiority. A one-sided 95% confidence interval for the mean difference between intervention groups will be completed using parametric methods if possible; otherwise, the median difference will be utilized.

Non-inferiority will be determined if the upper bound of the difference indicative of treatment benefit in the control group is less than the MCID for each endpoint. No adjustment for multiple comparisons is necessary since all tests must be significant to determine non-inferiority (intersection-union multiple testing rule) for effectiveness.

9.11.2 Safety hypothesis (Non-Inferiority Test)

The tele-rehab intervention will be non-inferior to traditional PT at 12 weeks using the following endpoints at 12 weeks:

- Pain: The minimal perceptible clinical improvement difference (MCID) for non-inferiority will be 1.7
- Re-hospitalizations: The total number of re-hospitalizations will differ by no more than 1.
- Falls: The percentage of subjects reporting any fall from index hospital discharge until 12 weeks postoperative will differ by no more than 10% (reported at 6 and 12 weeks as a categorical yes/no response).

A one-sided 95% confidence interval for the mean difference between intervention groups will be completed using parametric methods if possible; otherwise, the median difference will be utilized. Non-inferiority will be determined if the upper bound of the difference indicative of a treatment benefit in the control group is less than the MCID for each endpoint. No adjustment for multiple comparisons is necessary since all tests must be significant to determine non-inferiority (intersection-union multiple testing rule) for the safety hypothesis.

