1.3. Rationale for VERITAS Randomized Controlled Trial

The use of digital technology where the patient and therapist can interact both in real-time and asynchronously (e.g., patient completes recommended activities and therapist reviews performance at different times) can alleviate scheduling issues for both the therapists and patients, allowing therapists to potentially manage more patients (higher case load) and patients to follow recommendations and complete activities when most convenient. Having the PT program entirely available to the patient via technology may be cost efficient for both the patient and health system as more therapy sessions could be completed by the patient on their own schedule, without co-pays, and requiring less real-time PT supervision over time. The primary aim of this project is to determine if a technology-supported home-based PT rehabilitation program is a cost-saving approach and at least clinically equivalent to traditional PT.

2. Study Aims

The goals of this research study are the following:

1. To compare the effects of tele-rehab-supported PT versus traditional home and/or clinic-based PT for TKR on 90-day health service use costs.
Hypothesis (Superiority): Patients who receive tele-rehab-supported PT will have lower total 90-day episode of care costs compared with patients in the traditional PT group.
2. To compare tele-rehab-supported PT and traditional PT on patient-centered outcomes
 - a. Effectiveness hypothesis (Non-Inferiority): The tele-rehab intervention will be non-inferior to traditional PT at 6 weeks (differences between groups <5% for clinical and patient-reported outcomes) and 12 weeks (difference <5% patient-reported outcomes).
 - b. Safety hypothesis (Non-Inferiority): The tele-rehab intervention will be non-inferior to traditional PT at 12 weeks (pain, self-reported number of re-hospitalizations and number of reported falls).
3. To explore whether individual patient characteristics are associated with differential improvement from 6 to 12 weeks assessed by patient-reported outcomes.

3. Study Design

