7.2.3 Secondary Endpoints Compared at 12 Weeks Postoperative for Non-inferiority

At approximately 12 weeks after surgery, the patient will be contacted again by the DCRI Call Center to collect the following data via telephone interview:

Non-inferiority effectiveness endpoints:

1. Survey regarding health (KOOS)

Non-inferiority safety endpoints:

1. Pain score
2. Any fall reported between hospital discharge and 12-week follow-up (yes/no)
3. Re-hospitalizations since hospital discharge (total count)

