7.3 Additional Secondary Endpoints

Additional secondary endpoints are collected at 6 and/or 12 weeks post-operatively that are not part of non-inferiority testing for effectiveness or safety. Superiority testing will be completed for all non-inferiority endpoints and these additional secondary endpoints below.

Endpoints collected and compared at 6 weeks:

1. KOOS subdomain scores
2. Physical activity (duration of moderate exercise in total minutes per week)
3. Return to work by 6 weeks (yes, modified schedule, or no)

Endpoints collected and compared at 12 weeks:

1. KOOS subdomain scores
2. Patient-Reported Outcomes Measurement Information System (PROMIS) – Physical Health (PH)
3. Patient-Reported Outcomes Measurement Information System (PROMIS) – Mental Health (MH)
4. Satisfaction with Physical Function (questionnaire)
5. Physical activity (duration of moderate exercise in total minutes per week)
6. Return to work by 12 weeks (yes/modified schedule/no)
7. Satisfaction with tele-rehab platform (*intervention patients only thus just tabulated*)

Endpoints collected at both 6 weeks and 12 weeks post-operatively but compared only at 12 weeks (*patient diary and interview data that need to be combined to represent the entire 12 weeks*):

1. Adherence to prescribed PT regimen (# days per week, adherence [5 categories], and reasons for not done as prescribed)
2. Healthcare encounters – 8 types (total PT visits, calls/emails to PT, MD office visits, MD phone calls/emails, re-hospitalizations, urgent care or ER visit, inpatient re-habilitation stay, and skilled nursing facility stay)
3. Progress toward personal recovery goal [actual score, score=10 (yes/no), and time to meeting goal]

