9.8 Follow-up Data Collection Forms

9.8.1 6-Week Data Collection

Standard clinical follow-up for TKR patients occurs approximately 6 weeks after surgery. At this routine visit, patients will be administered standard clinical assessments for gait speed and range of motion (ROM) in the operated knee. Six-week data captured will

include the time from surgery until the date of the 6-week visit in days. Ten-meter gait speed and range of motion (ROM) upper and lower scores will be tabulated overall and by treatment group. Comparisons between treatment groups will be based on an analysis as described Sections 9.11 and 9.12.

9.8.2 6-Week Patient Survey

The DCRI call center captures patient-reported outcome measured 6 weeks after surgery, including fallen since hospital discharge (yes/no), pain score, physical activity (frequency and duration of exercise) and return to work (yes/no, and if yes, same or modified schedule). These 6-week variables will be summarized overall and by treatment group.

The KOOS Knee Survey Questionnaire will also be administered at 6-weeks. Responses will be tabulated overall and by treatment group for each question response as well as for the total score; however, no statistical comparisons will be done on the individual responses. The KOOS junior can be used at the 6-week visit. The overall KOOS score will be evaluated for both superiority and non-inferiority at 6-weeks, while the KOOS subdomain scores will only be compared for superiority as part of the exploratory analyses.

9.8.3 3-Month Patient Survey

At this visit, patients will be again be contacted by the DCRI call center to capture patient-reported outcomes, including fallen since last interview (yes/no), pain score, total re-hospitalizations since discharge, physical activity (frequency and duration of exercise) and return to work (yes/no, and if yes, same or modified schedule).

Additional survey data collected will include the Satisfaction with Physical Function Survey, the PROMIS Global Health Survey, the PROMIS Global Mental Survey, and the KOOS Knee Survey Questionnaire. Responses will be tabulated overall and by treatment group for each question response; however, no statistical comparisons will be done for the individual responses. The overall KOOS score and individual subscale scores will be compared. The KOOS junior cannot be used at the 3 month time point for efficacy analysis but can be used to evaluate change from 6 weeks to 3 months.

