The Net Promoter Score (how likely it is that you would recommend virtual physical therapy) will also be summarized within the subjects randomized to virtual rehab on a scale from 0 (not likely) to 10 (likely).

Additional variables collected at both 6- and 12-weeks but compared only at 12-weeks include healthcare encounters, adherence to prescribed PT regimen ((# days per week, adherence [5 categories], and reasons not done as prescribed) and progress toward personal recovery goal will be summarized using both categorical and continuous variables. Each type (PT visit, PT call/email, doctor visit, doctor call/email, urgent care visit, ER visit and hospitalization) will be summarized as incidence rate (Yes/No) and the number of encounters.

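### The re-hospitalization margin of 1 has no stated scale: read per patient it cannot exclude a meaningful excess, and read as arm totals it can hardly be met

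*SAP*

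**What the plan says.** Protocol Section 2, aim 2b, names the "self-reported number of re-hospitalizations and number of reported falls" among the 12-week safety outcomes. SAP 7.2.3 carries re-hospitalization forward as a total count, and SAP 9.8.3 lists "total re-hospitalizations since discharge" among the items each patient reports.

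SAP 9.11.2 sets the margin: "The total number of re-hospitalizations will differ by no more than 1". The statistic compared with it is the upper limit of a one-sided 95% interval for the mean difference, "using parametric methods if possible; otherwise, the median difference will be utilized". All three components (pain, re-hospitalization, falls) must pass, so no multiplicity adjustment is made. The falls margin in the same list does state its scale: a percentage of subjects.

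SAP Section 10 says the margins rest on literature and clinical experience. Section 12 gives sources only for KOOS, pain and range of motion. Neither document gives an expected re-hospitalization rate, a variance or a power for this endpoint.

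**The concern.** A count margin needs a denominator. The prescribed interval is for a difference in means or medians of a patient-level variable, so 1 reads as one extra re-hospitalization per patient within 12 weeks. The words total number, on the other hand, can be read as the sum over an arm, where 1 is 1/150 of an admission per patient. The two readings differ by a factor of 150 and have opposite defects.

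At stake is what a safety conclusion would mean. Under the per-patient reading it would name re-hospitalization although that component had excluded nothing of interest. Under the arm-total reading the safety claim would usually fail even if the arms were identical. If the reading is chosen after the data are seen by arm, that choice could decide the result.

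**Working it through.** **Inputs.** From the documents: margin 1 and the bound rule (SAP 9.11.2); one-sided 0.05 (SAP Section 9); 150 per arm (SAP 9.9); $7,825 per stay, defined as "Full length of one inpatient stay" (SAP 9.10). Assumed, because the documents give none: re-hospitalization rates per patient over 12 weeks, and Poisson counts unless stated.

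**1. The plan's own power figure.** It concerns cost only. With effect size 0.3245 and 150 per group, the noncentrality is 0.3245 × √(150/2) = 2.810. The noncentral t with 298 df gives 80.0% power, so the figure reproduces. There is no corresponding figure for re-hospitalization.

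**2. Per-patient scale, mean branch.** Upper bound = (rT − rC) + 1.645 × √((rC + rT)/150), with rC = 0.05.

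- Equal rates: 1.645 × √(0.10/150) = 0.043.
- rT = 0.50: 0.45 + 1.645 × √(0.55/150) = 0.45 + 0.100 = 0.550. A tenfold rate lies well inside a margin of 1.

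Probability of declaring non-inferiority (20,000 simulated trials, Welch interval):

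| Control mean | rT 0.10, 0.25, 0.50 | 0.80 | 0.90 | 1.00 |
|---|---|---|---|---|
| 0.03 | 100% | 91% | 50% | 11% |
| 0.05 | 100% | 94% | 59% | 16% |
| 0.10 | 100% | 98% | 78% | 32% |

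With variance five times the mean and control 0.05: 100% at 0.25, 95% at 0.50, 49% at 0.80.

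**3. Per-patient scale, median branch.** SAP 9.10 chooses between parametric and rank methods by normality checks and transformation, and 9.11.1 says the non-inferiority analyses of effectiveness are similar; 9.11.2 uses the same parametric-or-median wording. For simulated counts at 0.05 v 0.10, the Shapiro-Wilk test rejected raw, log and square-root data in 1,000 of 1,000 trials, so this branch is likely. The SAP does not name the interval for the median difference; I take it as Hodges-Lehmann.

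Counts are whole numbers, so the bound is below 1 only if fewer than K of the 150 × 150 = 22,500 patient pairs favour control by at least 1:

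K = 11,250 − 1.645 × √(22,500 × 301/12) = 11,250 − 1,236 = 10,014, or 44.5% of pairs.

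| rT (control 0.05) | Expected share of pairs | Declared non-inferior |
|---|---|---|
| 0.40 | 31.7% | about 100% |
| 0.50 | 37.9% | about 96% |
| 0.60 | 43.5% | about 60% |
| 0.70 | 48.6% | about 15% |
| 0.80 | 53.3% | about 1% |

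**4. Arm-total reading.** The margin is 1/150 = 0.0067 per patient. Power at equal rates r is Φ(0.0067/√(2r/150) − 1.645).

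| r | Standard error | Power | Per arm for 80% power |
|---|---|---|---|
| 0.02 | 0.0163 | 10.8% | 5,565 |
| 0.05 | 0.0258 | 8.3% | 13,911 |
| 0.10 | 0.0365 | 7.2% | 27,822 |
| 0.15 | 0.0447 | 6.7% | 41,733 |

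**5. What else would show an excess.** Two-sided superiority testing at 0.05 (Welch) has about 35% power for 0.05 v 0.10, 80% for 0.05 v 0.15 and above 99% for 0.05 v 0.25. In the cost endpoint, an excess of 0.20 per patient adds 0.20 × $7,825 = $1,565 per tele-rehab patient.

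**The case against.** The strongest reply is that a real excess would not go unseen. SAP 7.3 states "Superiority testing will be completed for all non-inferiority endpoints and these additional secondary endpoints below", and SAP 9.8.3 says each encounter type "will be summarized as incidence rate (Yes/No) and the number of encounters". The primary cost endpoint charges every re-hospitalization and is tested two-sided. This stands for gross excesses. But neither analysis changes the non-inferiority verdict, and the superiority comparison would miss a doubling from 0.05 to 0.10 about two times in three.

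A second reply is that sparse counts would probably go to the median branch, which is stricter than the mean branch at high rates. That is correct, and it limits the claim. A reader might infer that the component can fail only at nearly one extra admission per patient, or that totals of 8 v 138 would pass. Both hold on the mean branch only: (138 − 8)/150 + 1.645 × √146/150 = 0.999. A reader might also think the fallback equally lax because both sample medians stay at 0 while fewer than half of each arm is re-hospitalized. The rule uses an upper bound, though, not the sample medians, and on the Hodges-Lehmann bound the component starts to fail at tele-rehab means of about 0.5 to 0.6.

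Third, every rate here is assumed. True, but the result changes little over control means of 0.03 to 0.10, and strong overdispersion still leaves 95% passing at 0.50 on the mean branch.

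**Conclusion.** The concern holds in this form: the scale is undefined, and neither reading gives a usable test. The missing scale is certain from the text. The sizes rest on 150 analysed per arm, assumed rates, mostly Poisson counts and, for the median branch, a Hodges-Lehmann interval.

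Per patient, a tele-rehab mean of 0.40 against 0.05, eight times the control rate, passes essentially always on either branch. As arm totals, two identical arms would pass about 7-11% of the time.

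The documents do not support going further. This is one of three components of a secondary hypothesis; pain and falls must still pass, so the safety claim is not guaranteed by this margin. The primary cost test and its sample size are untouched. The point should be fixed, but it does not threaten the trial's main result.

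**What to change.** Amend the SAP, with an entry in Section 10, before database lock and without sight of data by arm:

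1. State that the scale is per patient.
2. Replace 1 with an absolute margin that the sponsor justifies in writing. It may apply to the difference in mean count, with a Poisson or robust interval, which keeps the count endpoint of aim 2b. Or it may apply to the difference in the proportion with at least one re-hospitalization, with a one-sided 95% Newcombe or Miettinen-Nurminen bound, declared as a change of endpoint form.
3. Do not use the median-difference fallback for this endpoint.

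No new data are needed, since SAP 9.8.3 already plans both the count and the yes/no form. Subjects, investigators and sponsor know the assignments (SAP 7.5), so the record must show that the margin was set blind to results by arm.

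The cost is power (150 per arm; margins illustrative, not proposals):

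| Scenario | Margin 0.10 | 0.075 | 0.05 |
|---|---|---|---|
| Mean count, equal at 0.05, Poisson | 98% | 89% | 62% |
| Same, variance twice the mean | 86% | 70% | 48% |
| Mean count 0.05 v 0.10, Poisson (still passes) | 49% | 22% | 6% |
| Proportion, equal at 5%, Newcombe | 98% | 88% | 60% |
| Proportion 5% v 10% (still passes) | 48% | 20% | 5% |

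Because all three components must pass, the power of the whole safety hypothesis cannot exceed these figures. A margin of 0.10 would still pass a doubling about half the time, so the choice needs an explicit argument.

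If the database is already locked, keep the planned test, report the replacement as post hoc, and say that the planned component could not exclude a meaningful excess.
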